Chapter 1

VATS Protocol

Table of Contents

1.	Introduction
2.	Objectives
3.	Patient Selection Criteria
4.	Registration and Randomization
5.	Product Preparation, Administration and Blinding
6.	Concomitant Medications
7.	Definitions and Endpoints
8.	Clinical and Laboratory Evaluations
9.	Study Parameters
10.	Forms Submission and Specimen Shipping Schedule
11.	Statistical Considerations
12.	References
Appendix I.	Model Consent Form
Appendix II.	Karnofsky Performance Scale

Section 1 -- Introduction

As many as 1.5 million Americans are currently infected with HIV-1.¹ Although there have been significant advances in development of relatively effective anti-retroviral therapies, as well as prophylactic and therapeutic strategies for prevention and/or treatment of several of the major opportunistic infections striking HIV-1-positive patients, these measures are only temporizing. Current estimates for the median time from infection to progression to end-stage disease (AIDS) range from 10 to 12 years,^{2,3} with survival following a diagnosis of AIDS averaging approximately two years.⁴ Prolongation in survival of HIV-1-infected patients is resulting in emergence of different manifestations of HIV-1-induced immunosuppression, including an increase in HIV-1-associated lymphomas, chronic wasting syndromes, and CNS manifestations.¹ These trends presage increased utilization of health care resources, including transfusion support,^{5,6} by HIV-1-infected persons over the next decade.

Virologically, the course of HIV infection represents progression through a series of dynamic phases.⁷ High levels of HIV-1 are present in the peripheral blood in the infected person early in infection prior to seroconversion.^{8,9} These levels fall dramatically with the development of neutralizing antibody and cell-mediated immunity.⁷⁻⁹ During the subsequent period of clinical latency, the concentrations of circulating virus in plasma and infected peripheral blood mononuclear cells are relatively low and stable,^{7,10-13} although viral replication in lymphoid tissues continues at a moderate-to-high level,⁷ resulting in turnover of up to 10^8 viral particles per day.¹⁴ This high turnover leads to rapid emergence of viral mutants that are resistant to immune and anti-viral control, and which may have enhanced virulence. Progression of disease correlates with increases in the concentration of circulating virus in plasma, as measured by end-point dilution cultures or quantitative RNA assays such as polymerase chain reaction (PCR) branched DNA (bDNA) analysis.^{7,10,12,13}

There is considerable variability in the length of the clinical latent period of HIV infection, and there has been much work to elucidate cofactors which govern progression of disease.^{2,3,7,15} There is extensive *in vitro*¹⁶ and *in vivo*¹⁷ evidence indicating that HIV-1 replication is highly dependent on the activation state of target lymphocytes. Whereas unstimulated lymphocytes infected with HIV-1 do not yield virus, substantial viral replication occurs after these cells are stimulated immunologically by antigens or mitogens. Recent studies of HIV-1 replication *in vivo* following a variety of immunological events, such as vaccinations,¹⁸ IL-2 infusions,¹⁸ and spontaneous herpes viral infections,¹⁸ have demonstrated significant increases in plasma viremia, presumably secondary to immune activation.¹⁹

There is also substantial evidence demonstrating that transfusion of allogeneic blood (particularly fresh, non-leukoreduced blood) results in immune activation.²⁰⁻²³ Data from animal models indicate that this immune activation can result in viral reactivation,²⁴ as well as immunomodulation leading to enhanced tumor recurrence and bacterial infection.^{22,25} In an *in vitro* study,²⁶ allogeneic donor leukocytes have been shown to induce reactivation of HIV-1 infection from peripheral blood mononuclear cells from HIV-1-infected persons, followed by dissemination of HIV-1 to uninfected cells. No effect was seen when leukocyte reduced blood components (packed red blood cells or platelets) were used in co-cultivation studies. These studies suggest that uninfected donor lymphocytes present in the transfused blood may activate HIV-infected and uninfected lymphocytes in the recipient, triggering an increase in viral replication and accelerating clinical progression.^{26,27}

Three retrospective studies have supported an adverse effect of transfusion on the course of HIV-1 infection.²⁸⁻³¹ Ward et al. found that the number of blood transfusions given at the time of HIV-1 infection correlated significantly with a shortened time to development of AIDS.²⁸ The second study showed that the number of transfusions given in early AIDS was associated with a shortened overall survival.^{29,30} In the third report, focused on patients with CD4 counts less than 250, Sloan et al. demonstrated that the incidence of clinically significant CMV infections correlated positively with the number of transfusion received.³¹ A problem in interpreting these retrospective studies is that, although the authors attempted to control for the stage of disease, transfusion could be a surrogate for poor prognosis. Recently, two small prospective studies were conducted to examine the short-term effects of transfusion on HIV viremia in HIV-1-infected persons. These studies showed only a modest rise in plasma p24 antigen and HIV-1 RNA levels (determined by quantitative RT-PCR and bDNA assays) several weeks following

transfusion, compared to control non-transfused patients or recipients of filter-leukoreduced blood.^{32,33} Of note, the blood transfused in these pilot studies was sub-optimal for inducing immune activation in the recipient: in one study only long-term refrigerated blood (>16 day storage) was used,³³ while the other study used irradiated blood components.³² Storage and irradiation are known to markedly reduce the immune cell function and immune modulating properties of transfusions.^{20,23,25,34-36}

Latent CMV infection may also be triggered to reactivate by transfusion, and this may be associated with contaminating allogeneic leukocytes in the transfused blood.^{24,37} Leukocyte-reduction of blood has been established to decrease the risk of transmitting CMV from seropositive donors to CMV-seronegative recipients.³⁸ However, only one small pilot study involving cardiac transplant patients has examined the effect of leukoreduction on CMV reactivation and disease in seropositive individuals; that study showed a reduction in clinically significant CMV manifestations in recipients of leukoreduced blood vs non-leukoreduced blood.³⁹ Although primary and reactivation CMV infections are usually asymptomatic in immunocompetent persons, they can be life-threatening for immunosuppressed patients. Indeed, CMV is the most common serious viral infection in AIDS patients and is associated with retinitis, colitis, esophagitis, hepatitis, encephalitis, and pneumonia. Nearly 100% of homosexual men and injection drug users with HIV-1 infection have serological evidence of CMV infection, and more than half shed CMV in the urine or semen. As noted above, the retrospective study by Sloan, et al.³¹ found a significant increase in CMV-related morbidity and mortality in HIV-1 infected persons following transfusion. Although the direct effect of allogeneic transfusions on CMV viremia in HIV-infected patients has not been studied in detail, preliminary data generated for this study show a several-fold increase in CMV DNA levels in leukocytes during the week post-transfusion in several HIV-positive recipients.³³

Transfusion-associated graft-versus-host disease (TA-GvHD) occurs in immunocompromised persons who are transfused with blood containing viable allogeneic lymphocytes, i.e. non-irradiated blood stored at 4°C less than 2 weeks.⁴⁰⁻⁴² TA-GvHD has been described in individuals with bone marrow transplants, congenital immune deficiency states, and in some cancer patients. Recently TA-GvHD has been reported in immunocompetent individuals who receive blood from family members with closely related HLA type, or from donors who, by chance, share an HLA haplotype with the recipient.^{41,42} Data also suggest that donor lymphocytes proliferate transiently in immunocompetent recipients, apparently in an abortive GvHD reaction.²³ Adequate gamma-irradiation of blood products eliminates this risk. The American Association of Blood Banks recommends irradiation of all blood transfused to individuals with these underlying diseases, as well as to persons receiving blood from closely related persons. Surprisingly, TA-GvHD has not been reported in AIDS patients.^{43,44} This may be because cases of TA-GvHD in AIDS patients go unrecognized because many of the clinical manifestations of GvHD regularly occur in late stage HIV-1 infection. Alternative explanations for the absence of TA-GvHD in AIDS patients include rapid infection and destruction of proliferating alloreactive donor lymphocytes by HIV,⁴³ or failure of the HIV-infected patient's immune system to contribute effector cells to the GvHD immunopathological process.^{44,45} No studies have been reported to date that directly examined persistence of donor leukocytes in HIV-infected transfusion recipients.

Current transfusion practice for HIV-1-positive patients varies widely and is highly controversial.^{5,6} Although theoretical arguments for allowing autologous donations by HIV-1-positive patients (when possible) are compelling,⁴⁶ concerns over possible transfusion error as well as the infectious exposure of blood bank and hospital personnel has led FDA to discourage this practice. Recent studies showing that erythropoietin (EPO) can reduce blood utilization in HIV-1-infected patients are promising.⁴⁷ However, these studies indicate that EPO is most effective in mild anemias and rarely eliminates the need for all allogeneic blood in HIV-1-positive patients; EPO is also expensive. Consequently, transfusion of allogeneic blood components will probably continue to be the major modality for managing HIV-1-associated anemia and thrombocytopenia for the foreseeable future.^{5,6}

Unfortunately, there is currently a lack of consensus on how best to manage allogeneic transfusion support of HIV-1-infected patients. In a recent AABB survey of institutions with large HIV-patient populations, 36% of hospitals routinely use leukoreduced blood for all HIV-positive patients, 28% routinely irradiate all blood, and 20% use CMV-negative blood for all HIV-positive patients irrespective of recipient CMV status. Although there are no known adverse effects from the use of CMV negative blood components, CMV negative donors are limited in number and, depending on the region, vary from 50% to less than 10% of the population³⁸. The use of filters for leukocyte reduction appears to be relatively safe although rare reactions to the filters, characterized by severe hypotension and respiratory distress, have been recorded⁶⁴. The cost of such specialized component support is substantial, and will grow as more HIV-positive patients require transfusion. Clearly, data are needed to guide policy in this area.

The present study is designed to determine if transfusion of allogeneic blood to HIV-1-infected persons leads to immune activation and consequent induction of HIV-1 and/or CMV replication, and whether this adversely affects clinical prognosis. The study will determine the role of donor leukocytes in producing this activation by examining the effect of removing leukocytes by filtration on viral induction and clinical progression. Finally, the study will examine the long-term persistence of circulating donor lymphocytes after transfusion to determine if occult GvHD may be a significant occurrence in AIDS patients.

The study will be a multicenter randomized clinical trial including approximately 640 HIV-1-infected patients. Patients scheduled for transfusion will be entered into the study at the time of their first transfusion and randomized to one of two arms: unmanipulated (i.e., non-leukoreduced and non-irradiated) red blood cells or filter-leukoreduced red blood cells. Patients will receive all blood components treated in this way for a period of one to three years. The effect of repeated transfusions, if needed, will also be assessed. Blood samples will be taken from the individuals before transfusion and at varying intervals after transfusion. These samples will be studied using the polymerase chain reaction and branched DNA technology and, in selected cases quantitative cultures, to determine if activation of HIV-1 or CMV occurs following transfusion.⁴⁸⁻⁵³ Serial samples will also be tested for a number of immunological markers to measure immune activation.⁵⁴⁻⁵⁶ Lymphocyte survival kinetics will be examined in a subset of patients (i.e., female recipients of male blood) by allele-specific PCR assays.²³ Tests will also be performed on specimens collected at intervals when the patient is not being transfused to determine the stability of

values at baseline. The individuals will be examined clinically on a regular basis and monitored for incidence and recurrence of opportunistic diseases and overall survival.

Section 2 -- Objectives

2.1. Primary Objectives

In patients with HIV requiring RBC transfusion, to compare leukocyte reduced RBC versus non-leukoreduced RBC transfusions with respect to:

2.1.1. Overall Survival

2.1.2 Change in HIV viremia at first transfusion, as measured by RNA PCR, from pre-transfusion level to the level one-week post transfusion.

2.2. Secondary Objectives

In Patients with HIV requiring RBC transfusion, to compare leukocyte reduced RBC versus non-leukoreduced RBC transfusions with respect to:

2.2.1. Time to death or first new serious HIV-related complication.

Endpoints include selected new AIDS defining conditions and serious bacterial infections. The criteria for selection were that the condition has a median survival of less than one year or an acute mortality of >5%. Additionally, in most cases only definitively diagnosed conditions were selected.

These diseases include: disseminated fungal infections (cryptococcus, coccidiomycosis, histoplasmosis), invasive cervical carcinoma, cryptosporidium, CMV disease, visceral Kaposi's sarcoma, lymphoma, progressive multifocal leukoencephalopathy (PML), disseminated *Mycobacterium avium* complex or atypical mycobacterium, tuberculosis, *Pneumocystis carinii* pneumonia, toxoplasmosis and bacterial infections of a normally sterile site (bloodstream, CSF, etc.). See Section 7.5 for details.

2.2.2. Time to new CMV end organ disease, in patients with no prior CMV disease. Incidence of new CMV end organ disease or progression of existing CMV disease, in patients with prior CMV disease.

2.2.3. Among patients with detectable CMV viremia, change in quantitative CMV from pre-transfusion level to one-week post transfusion level. Among patients with non-detectable CMV viremia, percent positive after transfusion, and CMV level in those who do become positive.

2.2.4. Slope of HIV & CMV viral load over time, excluding 28-day periods after initiation of each transfusion episode. This endpoint will measure the long-term effect on viral load, excluding the immediate post-transfusion periods.

2.2.5. Incidence of individual HIV-related complications and infections described in Section 7.5.

2.2.6. Change in cytokine and lymphocyte activation marker levels from baseline to one week: TNF, TNF receptor, IL-6, β_2 M.

2.2.7. Change in lymphocyte markers, including CD4, CD8 and activated subsets (CD8+CD38+, CD8+HLA-Dr+).

2.2.8. Functional status (Karnofsky) and quality of life.

2.2.9. Persistence of donor lymphocytes in the recipient at one and three months after initial transfusion.

2.2.10. Area under the curve (AUC) of HIV and CMV viral load over 3-months post transfusion.

2.2.11. Other measures of change in viral load, such as change from baseline to mean level over weeks

1 - 4, change from baseline to individual time points, and area under the curve adjusted for baseline level.

- 2.3. Other analyses will explore the associations between laboratory-based biological end points and clinical outcomes.

Section 3 -- Patient Selection Criteria

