11.1 Design

This trial will be a two-group, double-blind, randomized trial comparing standard non-leukoreduced red blood cell (RBC) transfusions with leukoreduced RBC transfusions in 640 patients. Randomization will be stratified by CD4 history (or total lymphocyte count; see below) and by CMV end organ disease. All patients must be CMV seropositive.

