11.3 Analysis Plans

The primary analysis for the time-to-event endpoint will be the logrank test. The primary analysis for the change in viral load will be the t-test. In other analyses proportional hazards models will be used to adjust treatment comparisons for covariates and to explore the effects of covariates themselves. Short-term changes in viral load will be based on log change from baseline, using two-sample t-tests or a Wilcoxon test if Normal assumptions are violated even after transformations. Covariates will be incorporated using Analysis of Variance. Random effects models will be used to analyze slopes of cytokines, lymphocyte markers and viral load over time. Incidence of individual events will be summarized by calculating number of events per Person-year and compared with Poisson methods. For example, the number of new diagnoses of CMV end organ disease, or diagnoses of CMV progression, will be counted and divided by the number of person-years of followup in order to estimate an incidence rate for CMV events, and compared with Poisson methods. (Note that a single person can have more than one CMV event.) In addition, person-specific incidence rates for each of several event types will be compared with two-sample Wilcoxon tests. The test statistics can be combined into an overall test using methods of Wei and Johnson⁶⁶.

Section 12 -- References

1. Centers for Disease Control: 1993 revised classification system for HIV infection and expanded surveillance case definition for AIDS among adolescents and adults. *MMWR* 1992;41(RR-17):1-19.

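### Objective 2.2.3 compares CMV level between arms only in patients who become positive after transfusion, a post-randomization selection that can shrink a true benefit and, in some settings, reverse it

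*Protocol*

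**What the plan says.** The lead-in to Protocol section 2.2 says that the listed items serve "to compare leukocyte reduced RBC versus non-leukoreduced RBC transfusions with respect to" each item. Item 2.2.3 splits patients by whether CMV is detectable before transfusion. For the non-detectable group it lists two quantities: "Among patients with non-detectable CMV viremia, percent positive after transfusion, and CMV level in those who do become positive".

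The Introduction says that the study asks whether transfusion "leads to immune activation and consequent induction of HIV-1 and/or CMV replication", and what removing donor leukocytes does to this. It also says "Latent CMV infection may also be triggered to reactivate by transfusion" and links this to leukocytes in the transfused blood. Section 11.1 adds "All patients must be CMV seropositive", so the population as a whole is at risk of reactivation.

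Section 11.3 says "Short-term changes in viral load will be based on log change from baseline, using two-sample t-tests or a Wilcoxon test". It does not mention the selection into the converter group, and nothing in 2.2.3 or 11.3 marks the converter level as descriptive. Two other objectives give CMV measures that are not limited to converters: "Area under the curve (AUC) of HIV and CMV viral load over 3-months post transfusion" (2.2.10), and in 2.2.11 "change from baseline to individual time points, and area under the curve adjusted for baseline level".

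**The concern.** The split by baseline detectability is fixed before randomization and is harmless. The second restriction, to those who become positive, is not. If the trial's hypothesis is right, some patients convert with non-leukoreduced blood who would not have converted with leukoreduced blood. The control converters then include a kind of patient that is missing from the leukoreduced converters, and a difference in mean level mixes the treatment effect with this difference in composition.

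The comparison is least reliable when the treatment works. If the prevented conversions are mostly low-level, the remaining leukoreduced converters have a higher average level, and a benefit can be reported as a higher CMV level in the leukoreduced arm.

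**Working it through.** **Inputs.** The protocol states no conversion rate, CMV level, SD, assay limit or share of patients non-detectable at baseline, and no power for this endpoint. There is no figure of its own to reproduce. Everything below is assumed and shown as a range.

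**1. Two levels of conversion.** Assume that 20% of controls convert at a mean of 2.3 log and 10% at a mean of 3.8 log.

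- Control converters: (0.20 × 2.3 + 0.10 × 3.8) / 0.30 = 0.84 / 0.30 = 2.80 log.
- Leukoreduced, only the low-level conversions halved: (0.10 × 2.3 + 0.10 × 3.8) / 0.20 = 0.61 / 0.20 = 3.05 log. The difference is +0.25 log against leukoreduction, although conversion fell from 30% to 20% and nobody was harmed.
- Leukoreduced, both types halved: (0.10 × 2.3 + 0.05 × 3.8) / 0.15 = 0.42 / 0.15 = 2.80 log. The difference is 0.00.

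Simulating the first case with a two-sided 5% t-test on converters gives these approximate rejection rates, nearly all in the wrong direction:

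| Baseline-non-detectable per arm | SD 0.2 | SD 0.3 | SD 0.5 | SD 0.8 |
|---|---|---|---|---|
| 250 (500/640 = 78% of patients) | 44% | 42% | 36% | 24% |
| 100 (200/640 = 31% of patients) | 21% | 20% | 17% | 12% |

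With both types halved, the rejection rate stays near the nominal 5%.

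**2. Uniform shift.** Let log CMV be normal with SD 1 and let leukoreduction lower every patient by d. With the assay limit at 0, the mean in positives is μ + φ(μ)/Φ(μ). For control positivity of 16% to 50%:

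| True shift | Difference seen in positives |
|---|---|
| −0.15 | −0.03 to −0.05 |
| −0.30 | −0.06 to −0.10 |
| −0.70 | −0.12 to −0.21 |

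The sign is right, but most of the effect is lost.

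**3. Always and induced converters.** A share pa converts in either arm, with a mean of 3.0 log in controls. A share pi converts only with non-leukoreduced blood, at a level lower by g. Leukoreduction lowers the level of the always-converters by e. Then

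leukoreduced minus control = g × pi/(pa + pi) − e,

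and the sign is wrong whenever the first term exceeds e. Take pa = 0.10 or 0.20, pi = 0.05, 0.10 or 0.20, and g = 0.5 or 1.0 (12 settings). The first term runs from 0.5 × 0.05/0.25 = 0.10 to 1.0 × 0.20/0.30 = 0.67.

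- e = 0: +0.10 to +0.67.
- e = 0.15: −0.05 to +0.52, wrong sign in 11 of 12.
- e = 0.30: −0.20 to +0.37, wrong sign in 6 of 12.

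**4. All baseline-non-detectable patients, non-detects ranked lowest.** For pa = 0.10, pi = 0.10, g = 1.0, e = 0.15 and SD 0.5, the converter-only difference is 0.50 − 0.15 = +0.35 log, the wrong sign. The probability that a leukoreduced patient ranks above a control, counting half of ties, is 0.453. That is below 0.5 and so has the right sign.

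**5. Power.** In the first case of step 1 at 250 per arm, the all-patient rank test has about 61% to 65% power. A chi-square test on percent positive has about 72% to 75%.

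**The case against.** The strongest reply is that the sound comparison already stands in the same sentence. Percent positive uses all baseline-non-detectable patients, and in the illustrated setting it has more power than the rank test. Objectives 2.2.10 and 2.2.11 add CMV measures not restricted to converters. Fewer conversions with a higher mean among the rest is also a coherent result for a reader who looks at both numbers. All of this stands, and it limits the importance of the point. It does not repair the converter clause, which would still be reported as a comparison of the arms. The protocol also does not say how non-detects enter the other measures.

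A second reply is that no test on converters is specified. Section 11.3 speaks of log change from baseline, and these patients have no measured baseline level. The choice of test may be in an SAP that is not shown. That is fair, and the t-test in the working is an assumption. But the restriction to converters is written into the objective, and choosing a test does not remove it.

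A reader might infer that leukoreduced converters will look worse. The documents do not support this. Reversal needs the prevented conversions to be mainly low-level, and nothing in the protocol says that they are. A reader might also infer that the two parts of 2.2.3 cannot validly be combined. They can, by a rank or censored-data analysis of the same measurements.

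**Conclusion.** The point holds as a risk of selection bias in one component of objective 2.2.3. The protocol expects treatment to affect who becomes positive, so the level among converters is not a randomized comparison. A uniform shift in level is attenuated. Prevention of mainly low-level conversions can reverse the sign, by about 0.25 log in the illustrated setting with wrong-way rejection in about 12% to 44% of trials. Equal prevention of both types produces no spurious difference. These sizes rest wholly on assumed rates, levels, SDs and numbers of baseline-non-detectable patients. The percent-positive component, the split by baseline detectability, the primary endpoints, the sample size and the stopping rule are unaffected. A modest wording correction is warranted.

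**What to change.** In section 2.2.3, for patients non-detectable at baseline:

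- Keep percent positive as the main comparison.
- Replace the converter-only level comparison with post-transfusion CMV level in all baseline-non-detectable patients, with non-detects tied at the lowest rank. Use a rank-sum test stratified by the randomization factors in section 4.2, or a left-censored normal model.
- Report level among converters by arm as description, without a between-arm test.

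The gain is a valid comparison of level, not more power. The cost is a change of wording. The quantitative CMV measurements are already collected under section 8.4.1, and no sample size or visit changes.
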